12 males and 8 females athletes $(19.9 \pm 2.4 \text{ years}; 167.3 \pm 7.6 \text{ cm} \text{ height}; 63.5 \pm 10.2 \text{ kg} \text{ body mass}; 27.5 \pm 6.7 \text{ kg} \text{ lean body mass}; 22.6 \pm 8.2\% \text{ body fat}; 22.6 \pm 2.3 \text{ kg·m}^{-2} \text{ BMI})$ from both team and individual sports were recruited for the study (Table 1). During the first laboratory visit, anthropometric and body composition assessments were performed to characterize the participant sample. Standing height and body mass were measured to the nearest 0.1 cm and 0.1 kg using a calibrated stadiometer and digital scale (Seca, Hamburg, Germany). Body composition was determined via multi-frequency bioelectrical impedance analysis (InBody 770; InBody Co., Seoul, South Korea). All measurements were conducted in the morning, with participants wearing light clothing and having abstained from exercise, food, and caffeine for at least 3 hours prior to testing.

Inclusion criteria were: (i) active participation in individual or team sports at a competitive level, (ii) age between [insert range, e.g., 18-30] years, and (iii) absence of any known medical or metabolic disorder. Exclusion criteria included: (i) history of cardiovascular, neurological, or musculoskeletal disorders within the past 12 months, (ii) known intolerance or hypersensitivity to caffeine or theanine, (iii) allergy to mannitol or other excipients used in capsule formulation, (iv) current use of prescription medications, and (v) physician-directed restriction of caffeine or theanine consumption.

[figure not shown]

Figure 1. Flowchart

The required sample size was estimated using an a priori power analysis (G*Power 3.1.9.7; Düsseldorf, Germany) for a repeated-measures ANOVA with four conditions (CAF, THE, CAF + THE, CON), assuming a moderate effect size (f = 0.25), $\alpha = 0.05$, and statistical power ($1 - \beta$) = 0.80. The analysis indicated a minimum required sample of 16 participants. To account for potential attrition or missing data, 20 athletes were recruited; all completed the study protocol.

Supplementation Protocol

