The normality of the data set was initially evaluated using the Shapiro-Wilk test. Subsequently, the assumption of sphericity was examined through Mauchly's test, with the Greenhouse-Geisser correction applied in cases where sphericity was violated. Differences in strength, aerobic endurance, and eye-hand coordination outcomes across the four supplementation conditions (CAF, THE, COM, and CON) were analysed using a one-way repeated-measures analysis of variance (ANOVA). When significant main effects were observed, Bonferroni-adjusted pairwise comparisons were conducted to identify specific between-condition differences. The magnitude of effects was quantified using partial eta squared (ηp^2), interpreted as small (0.10–0.24), moderate (0.25–0.39), or large (\geq 0.40). For pairwise comparisons, Cohen's d for repeated measures and corresponding 95% confidence intervals (CI95%) were reported and interpreted as trivial (<0.20), small (0.20–0.49), moderate (0.50–0.79), or large (\geq 0.80) (Cohen, 1992). All statistical analyses were performed using IBM SPSS Statistics version 30.0 (IBM Corp., Armonk, NY, USA) and statistical significance was accepted at $\alpha = 0.05$ (two-tailed). Graphical visualizations were generated with GraphPad Prism version 10.0 (GraphPad Software, San Diego, CA, USA).

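### On the plain reading, pairwise d and its interval are planned only after a significant omnibus F: other outcomes get no interval against placebo, and reported real effects are inflated when power is low

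*Combined protocol and SAP*

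**What the plan says.** The Statistical Analysis section compares the four conditions on each outcome with a one-way repeated-measures ANOVA at two-sided 0.05. It then sets a condition: "When significant main effects were observed, Bonferroni-adjusted pairwise comparisons were conducted to identify specific between-condition differences".

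Two kinds of effect size follow. The first carries no condition: "The magnitude of effects was quantified using partial eta squared". The second is tied to the pairwise step: "For pairwise comparisons, Cohen's d for repeated measures and corresponding 95% confidence intervals (CI95%) were reported".

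The section lists no other estimate of a treatment-minus-placebo difference, either standardised or in the units in which the outcomes are recorded (kgf, metres, per cent, pixels).

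Study Design speaks of several primary outcomes. The outcome sections describe at least ten measures: three strength scores, Yo-Yo distance and six eye-hand coordination metrics.

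**The concern.** The trial asks what caffeine, theanine and their combination do relative to placebo. That calls for an estimate with an interval for each contrast, whether or not a test is significant. Because d and its interval belong to comparisons that are run only after a significant F, the plain reading makes estimation conditional on significance. Two things follow.

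- **Missing intervals.** An outcome with a non-significant F is left with partial eta squared alone. A reader cannot tell whether caffeine did nothing or was measured too imprecisely to say.
- **Selection.** When power is modest, the F test is passed more often in data sets where the observed differences happen to be large. The real effects that do get reported are then too large on average. This carries over into meta-analyses and into the planning of later trials.

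With about ten measures, each meeting this condition separately, the results table would mix outcomes that have contrast estimates with outcomes that have none, sorted by p-value. The point concerns estimates, not the error rate of the tests.

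**Working it through.** **Inputs from the document.** Four within-athlete conditions, two-sided alpha 0.05, planning effect f = 0.25, power 0.80, stated minimum N = 16, and 20 athletes recruited, all of whom completed (Participants; Statistical Analysis).

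**Assumptions.** The document gives no within-athlete correlation r and no sphericity parameter. I take SD 1, compound symmetry (so sphericity holds), and r = 0.5, 0.67 or 0.8. Caffeine and the combination are raised by d over theanine and placebo. With d = 0.5 the means are 0.5, 0, 0.5, 0. Their SD about 0.25 is 0.25, so f = 0.25, the planning effect.

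**Step 1: the plan's own figure.** The noncentral F has λ = N·m·f²/(1 − r), with m = 4 and df 3 and 3(N − 1). The smallest N for 80% power is 24 at r = 0.5, 17 at r = 0.65, 16 at r = 0.67, 15 at r = 0.70 and 11 at r = 0.8. Check at N = 16, r = 0.67: λ = 16 × 4 × 0.0625/0.33 = 12.1, power 0.808. So 16 is reproduced under an unstated r of about 0.67, which makes that the middle case below.

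**Step 2: chance of a significant F at N = 20, d = 0.5.**
- r = 0.5: λ = 20 × 4 × 0.0625/0.5 = 10.0, power 0.729
- r = 0.67: λ = 5/0.33 = 15.2, power 0.899
- r = 0.8: λ = 5/0.2 = 25.0, power 0.989

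The complements, 27%, 10% and 1%, are the shares of such outcomes left with no pairwise estimate.

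**Step 3: size of the selection.** I simulated 40,000 trials per row with the uncorrected F. Inflation is the mean difference from placebo among trials with p < 0.05, divided by the mean over all trials, minus 1. The differences are raw differences with true SD 1. Caffeine and the combination have the same true mean, so the figures apply to either.

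| True d | r | F significant | No pairwise estimate | Mean, all trials | Mean, F significant | Inflation |
|---|---|---|---|---|---|---|
| 0.5 | 0.5 | 0.730 | 27% | 0.501 | 0.566 | 13% |
| 0.5 | 0.67 | 0.898 | 10% | 0.501 | 0.525 | 5% |
| 0.5 | 0.8 | 0.990 | 1% | 0.499 | 0.502 | 0.6% |
| 0.3 | 0.5 | 0.304 | 70% | 0.299 | 0.455 | 52% |
| 0.3 | 0.67 | 0.453 | 55% | 0.302 | 0.402 | 33% |
| 0.3 | 0.8 | 0.678 | 32% | 0.299 | 0.347 | 16% |
| 0.2 | 0.5 | 0.152 | 85% | 0.201 | 0.391 | 95% |
| 0.2 | 0.67 | 0.212 | 79% | 0.199 | 0.339 | 70% |
| 0.2 | 0.8 | 0.337 | 66% | 0.199 | 0.292 | 47% |

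Simulation error is a few percentage points in the d = 0.2 rows and smaller above them. The pass rates at d = 0.5 agree with Step 2.

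**Step 4: contrasts with no true effect.** In the same scenarios the theanine-placebo difference, truly zero, averages within 0.003 of zero among trials with a significant F, so it has no signed bias. If all four conditions are equal, about 5% of outcomes pass. Among those, the combination-placebo difference again averages about zero, but its absolute size averages 0.34, 0.28 and 0.22 at the three correlations, and the 95% interval covers the truth about 64% of the time.

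**Step 5: without the condition.** Over all trials the mean estimate equals the true value and the 95% interval covers about 95% in every row.

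**The case against.** An omnibus test followed by Bonferroni comparisons is conventional. As a rule for claiming significance it is not in dispute here.

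The wording leaves room. The sentence on d and its interval does not repeat the condition, so the sponsor may have meant it for every pair. That stands as a limit: the restriction is inferred from when the comparisons are run. It is still the natural reading, and nothing in the document provides for the other case.

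A reader might infer that a non-significant outcome gets no effect size of any kind. The document does not support that. Partial eta squared is unconditional, and condition means are neither promised nor excluded. If means were tabulated, a point difference from placebo could be recovered. A within-athlete interval could not, because it needs the SD of the paired differences.

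A reader might also infer that every reported effect is overstated. That is too strong. Once F is significant all pairs are compared, including small ones, and a truly null contrast has no signed bias. At the planning effect the inflation is about 5% at the correlation that reproduces the plan's N, and under 1% at r = 0.8. Men and women tested together, and strength scored as a mean of three attempts, could push r higher still. The large figures belong to small true effects, which are assumed values.

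Finally, preferring measured units to d is partly a reporting choice. It is secondary to the missing intervals.

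**Conclusion.** The concern holds in a limited form. On the plain reading, no pairwise d or interval against placebo is planned for an outcome with a non-significant F, and the unconditional partial eta squared does not fill that gap. For real effects, the estimates that are reported are selected upward by an amount set by power. The selection is negligible to modest at the planning effect (under 1% to 13%), about 16% to 52% at d = 0.3, and up to nearly double at d = 0.2.

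The missing intervals matter even where the bias is small: at d = 0.3, between 32% and 70% of outcomes would have none. These sizes rest on the assumed r, d, pattern of means and compound symmetry; none is given in the document. The planned tests are unaffected. This is a worthwhile, inexpensive improvement to the reporting, not a flaw that invalidates the analysis.

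**What to change.** Add to Statistical Analysis that, for every outcome and whatever the omnibus p-value, the pairwise mean differences (at least caffeine, theanine and the combination, each against placebo) are reported in measured units with 95% confidence intervals, plus d if wanted.

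State which intervals these are. Bonferroni-adjusted intervals match the planned pairwise tests: over six pairs, 0.05/6 = 0.0083 each, which already controls error within an outcome. Unadjusted intervals should be labelled as for estimation only. Keep the omnibus condition for statements of significance, and say that a non-significant result is interpreted from its interval.

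The cost is a few sentences and one larger table, with no new data. The drawback is that an interval may occasionally seem to disagree with the omnibus test, more readily if it is unadjusted, so the label is needed.

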STUDY PROTOCOL – COVER PAGE
Official Title:	
Acute Effects of Combined and Isolated Caffeine and Theanine Supplementation on Physical and Cognitive Performance in Competitive Athletes: A Randomized, Double-Blind, Placebo-Controlled Crossover Study	
Sponsor-Investigator:	
Assoc. [name] [name]	
Faculty of Sport Sciences, Sinop University, Türkiye	
[contact]	
Ethics Committee Approval:	
Sinop University Human Research's Ethics Committee	
Approval Number: 2025/337	
Approval Date: 22 May 2025	
Document Type:	
Study Protocol	
Version and Date:	
Version 1.0 – October 21, 2025	
Funding Source:	
Self-supported academic research	

Method

Study Design

This study employed a randomized, double-blind, placebo-controlled, crossover design to examine the effects of caffeine (CAF), theanine (THE), their combination (COM), and a placebo (CON) on physical and cognitive performance in young, healthy, competitive athletes. Each participant completed all four experimental conditions in a randomized order, with a washout period of at least 72 hours between sessions to minimize potential carryover effects. The randomization sequence was generated by an independent researcher using a computer-based randomization tool (Urbaniak & Plous, 2013). To ensure familiarity and minimize learning effects, all participants completed a familiarization session one week prior to the experimental trials. Physical and cognitive performance were assessed across multiple primary outcomes, including maximal strength, intermittent aerobic endurance, and eye-hand coordination. All procedures were conducted in accordance with the of Helsinki. The study protocol was approved by the Sinop University Human Research's Ethics Committee (Approval No: 2025/337), and all participants provided written informed consent prior to participation.

Participants

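### Pairwise step: replacing single-step Bonferroni with Holm would keep the 5% family-wise bound and recover a few points of power; an inexpensive improvement, not an error

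*Combined protocol and SAP*

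**What the plan says.** Under Statistical Analysis, outcomes "across the four supplementation conditions (CAF, THE, COM, and CON) were analysed using a one-way repeated-measures analysis of variance (ANOVA"). The pairwise step follows: "When significant main effects were observed, Bonferroni-adjusted pairwise comparisons were conducted to identify specific between-condition differences". The same section adds that "statistical significance was accepted at $\alpha = 0.05$ (two-tailed"). It names no step-down method and no subset of contrasts. It also promises Cohen's d with a 95% interval for each pair, without saying whether those intervals are adjusted.

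The sample size, under Participants, concerns the omnibus test only: it was obtained by "assuming a moderate effect size (f = 0.25") and "statistical power ($1 - \beta$) = 0.80", and "The analysis indicated a minimum required sample of 16 participants". No pairwise power is given. On conduct, Study Design states "Each participant completed all four experimental conditions in a randomized order", and Participants states "To account for potential attrition or missing data, 20 athletes were recruited; all completed the study protocol".

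**The concern.** The trial asks which of caffeine, theanine and the combination differ from placebo and from one another. The omnibus F cannot answer that; only the pairwise comparisons can. Those comparisons are reached only after a significant F, and every one of the six is then held to the strictest Bonferroni threshold, however many have already been rejected. Two logical facts make this stricter than it needs to be.

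- Holm gives the same strong control of family-wise error with thresholds that are never stricter than 0.05/6.
- If the four means are not all equal, at most three of the six pairwise nulls can be true. The F test already guards the case in which all are equal.

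At stake is some power at the step that carries the trial's conclusions, with 20 athletes and no pairwise power stated. The validity of any positive finding is not at stake.

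**Working it through.** **Inputs from the documents.** Four conditions, all received by each athlete; two-sided alpha 0.05; F gate, then Bonferroni; f = 0.25, power 0.80, stated minimum 16; 20 recruited and 20 completed.

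**Inputs assumed.** Within-subject correlation ρ (not stated; 0.5 to 0.8 tried), the pattern of true means, normality and, except where noted, sphericity.

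**1. The plan's own figure.** For a one-group repeated-measures F test with m = 4, λ = f²·N·m/(1 − ρ), df1 = 3, df2 = 3(N − 1). At ρ = 0.5 and N = 16, λ = 0.0625 × 16 × 4/0.5 = 8 and power is 61%; 80% needs N = 24. N = 16 results at ρ of about 0.67 to 0.68 (λ = 4/0.33 = 12.1). The stated 16 therefore cannot be reproduced from the stated inputs alone, but an unstated correlation could explain it, so it is not shown to be wrong. It has no bearing on pairwise power.

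**2. Thresholds.** Pairs = 4 × 3/2 = 6. For ordered p-values, smallest first:

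| Method | Divisors of 0.05 | First threshold | Last threshold |
|---|---|---|---|
| Plan (Bonferroni) | 6, 6, 6, 6, 6, 6 | 0.0083 | 0.0083 |
| Holm | 6, 5, 4, 3, 2, 1 | 0.0083 | 0.05 |
| Gate-aware Shaffer | 3, 3, 3, 3, 2, 1 | 0.0167 | 0.05 |

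Each row is at least as permissive as the one above it at every step, so the plan's rejections are always a subset of Holm's, and gated Holm's a subset of the gate-aware method's. For one pair at n = 20, the standardised paired difference detectable with 80% power is 0.86 at 0.0083 and 0.78 at 0.0167.

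**3. Family-wise error per outcome** (simulation, n = 20, 100,000 runs or more, sphericity):

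| True means | Plan | Gated Holm | Gate-aware |
|---|---|---|---|
| All equal | 3.0% | 3.0% | 4.3% |
| One far from three | 2.3% | 4.6% | 4.6% |
| Two against two, far apart | 1.6% | 4.9% | 4.9% |

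Under the complete null, gated Holm and the plan agree because their first steps are identical. Separate runs of the plan under that null gave up to 3.2%.

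**4. Power at the plan's f = 0.25.** The within-subject error SD is √(1 − ρ) of the total SD. At ρ = 0.66 that is 0.583. A two-against-two split then has a gap of 2 × 0.25/0.583 = 0.86 error SD. One condition differing has a gap of 0.25 × (4/√3)/0.583 = 0.99 error SD. Average power per real pair:

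| Pattern (ρ = 0.66) | Plan | Holm | Gate-aware |
|---|---|---|---|
| One differs | 57.8% | 61.8% | 68.0% |
| Two against two | 43.0% | 48.0% | 54.0% |
| Graded | 32.5% | 35.8% | 40.2% |
| Equally spaced | 26.6% | 29.5% | 33.3% |

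Over ρ = 0.5 to 0.8 the gain is about 2 to 6 points with Holm and about 6 to 11 with the gate-aware method. The power to find every real pair at ρ = 0.66 is 31.7%, 38.9% and 44.8% (one differs), and 10.7%, 18.8% and 19.4% (two against two).

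**5. Power at fixed assumed gaps**, with Greenhouse-Geisser applied only when Mauchly's test rejects, as planned (40,000 runs). Two against two, 0.8 error SD: 36.4%, 40.6%, 46.9%. One differing by 0.9 error SD: 47.3%, 50.6%, 57.8%. Holm's gains are 40.6 − 36.4 = 4.2 and 50.6 − 47.3 = 3.3 points.

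**6. At least one real pair.** With one condition differing at ρ = 0.66, gated: 81.9% under the plan, 81.9% under Holm, 87.1% under the gate-aware method. Holm cannot help here, because its first threshold is Bonferroni's.

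**The case against.** The strongest reply is that F-gated Bonferroni is valid and nothing in the documents contradicts it, so this is a choice among sound methods. That stands, and it fixes the status of the point. Several further objections also have weight.

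- **A reader might infer that the plan corrects twice for the same thing.** That is exact only when all four means are equal. The gate costs little (at most about 2 points of any-pair power); most of the loss comes from keeping divisor 6 at every step. Nor could the pairwise adjustment be dropped: gate plus unadjusted tests gave family-wise error of 12.5% with one condition far away and 9.7% with a two-against-two split.
- **A reader might infer that the power comes free at an unchanged error rate.** Only the 5% ceiling is unchanged. Actual error rises towards it when means are well separated, from 1.6% to 4.9% in the two-against-two case.
- **A reader might infer that real differences have been lost.** The documents report no results and the effect sizes here are assumed. In the 0.8 SD scenario even the most powerful method misses 53.1% of real contrasts (100 − 46.9), so the sample size is the larger limit. Pairwise effect sizes with intervals are planned as well.
- **Outcomes are not adjusted for one another.** This is true and separate. Counting ten measures (three strength, one endurance, six coordination) and assuming independence, the chance of at least one false-positive F test is 1 − 0.95^10 = 40%. Under complete nulls, the chance of a false pairwise claim on some outcome is 1 − 0.97^10 = 26% with the plan or gated Holm, and 1 − 0.957^10 = 36% with the gate-aware method.
- **Data collection is over.** A change now can only add significant pairs. Because the plan's rejections are a subset of the step-down ones, switching cannot breach the 5% bound within an outcome, but it must be disclosed.

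**Conclusion.** This is a low-cost improvement to a valid plan. Read as six pairs at 0.0083 behind an F gate, the procedure uses about 1.6% to 3.2% of a 5% family-wise allowance in the configurations tried. That Holm dominates it under the same bound follows from the thresholds and needs no assumption about effects.

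The size of the gain does rest on assumptions. It is about 3 to 4 points per real contrast at assumed gaps of 0.8 to 0.9 error SD, and about 2 to 6 points at f = 0.25 with an assumed correlation of 0.5 to 0.8. There is no gain in the chance of finding at least one pair. The gate-aware method gains about 6 to 11 points, but its validity depends on that of the F test, including the Greenhouse-Geisser correction when sphericity fails. Ungated Holm has no such dependence.

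**What to change.** In Statistical Analysis, replace the Bonferroni wording with Holm step-down adjustment over the six pairs, and report adjusted p-values. With p(1) ≤ … ≤ p(6), the adjusted p(j) is the largest of (7 − i)·p(i) over i ≤ j, capped at 1. If the F gate is kept, Shaffer's step-down with divisors 3, 3, 3, 3, 2, 1 may be named instead, as an option.

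State whether each 95% interval is adjusted or unadjusted, since step-down tests have no simple matching simultaneous intervals. Date the change, label it as made after all participants had completed, and show the Bonferroni results alongside.

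The cost is a sentence or two of text and a re-ranking of six p-values per outcome, with no new data. The plan names SPSS 30.0 but no step-down routine, so the adjustment may be done by hand from the paired p-values. Multiplicity across outcomes needs its own decision.
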